4.2 Analysis Plan for Secondary Aim: Potential

Recipient Activation We will explore the crosstab of scenario by study arm cross-sectionally at each time and comparisons will be made via a chi-squared or Fisher’s exact test as appropriate.

4.2.1 Continuous Formulation of Scenario

We will model scenario as a continuous variable and use longitudinal GEEs (normal outcome) with an unstructured correlation matrix to determine if the total scenario changes over time for each arm. Specifically, we will fit a model of the form

$$\begin{aligned} g(\mu) = & \beta_0 + \beta_1(\text{Arm2}) + \beta_2(\text{Arm3}) + \beta_3(4\text{mo}) + \beta_4(12\text{mo}) \\ & + \beta_5(\text{Arm2} \times 4\text{mo}) \\ & + \beta_6(\text{Arm3} \times 4\text{mo}) + \beta_7(\text{Arm2} \times 12\text{mo}) + \beta_8(\text{Arm3} \times 12\text{mo}). \end{aligned}$$

Because all the variables are indicator functions, the right hand side reduces to

	Arm 1	Arm 2	Arm 3
Baseline	β_0	$\beta_0 + \beta_1$	$\beta_0 + \beta_2$
4 months	$\beta_0 +$ β_3	$\beta_0 + \beta_1 + \beta_3 +$ β_5	$\beta_0 + \beta_2 + \beta_3 +$ β_6
12 months	$\beta_0 +$ β_4	$\beta_0 + \beta_1 + \beta_4 +$ β_7	$\beta_0 + \beta_2 + \beta_4 +$ β_8

We will assess the changes in scenario within each arm, and then determine if there is a difference across arms at 12 months. Note that the difference from baseline to 12 months within each arm is given by

	Arm 1	Arm 2	Arm 3
4 months - Baseline	β_3	$\beta_3 + \beta_5$	$\beta_3 + \beta_6$
12 months - Baseline	β_4	$\beta_4 + \beta_7$	$\beta_4 + \beta_8$

If β_7 is non-zero, the change from baseline in Arm 2 is significantly different than the change from baseline in Arm 1. Similarly, if β_8 is non-zero, the change from baseline in Arm 3 is significantly different than the change from baseline in Arm 1.

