A. Study population: We will recruit a total of **300 (100 per each study arm) adult African American patients with ESRD who are currently on the deceased donor kidney waiting list with no prior kidney transplant** from the Duke Kidney and Pancreas Transplant Program (DKPTP). The DKPTP cares for a highly diverse set of patients with ESRD, with nearly 55% of the deceased donor kidney transplant waiting list comprised of African Americans annually. As of January 2014, the DKPTP had 297 (55%) African American patients registered on the deceased donor kidney waiting list. DKPTP added approximately 100 new African American waiting list registrants per year in 2012 and 2013. African Americans on the deceased donor kidney waiting list at DKPTP are sociodemographically diverse, and reflect the local Durham, NC population in which 19% have incomes below the Federal Poverty Level. **50**

B. Study Setting: The kidney/pancreas transplant program at DKPTP is a highly innovative center, providing national leadership in the development and implementation of numerous clinical strategies to improve rates of live kidney donation and donor safety (performed first kidney transplant in NC and had performed their 3000th kidney transplant in 2010). The center also features a complete team of transplant surgeons, nurse transplant coordinators, administrative transplant coordinators, psychologists, and social workers to support both potential recipients' and donors' medical and psychosocial needs. The program currently does not have a social worker program tailored specifically to address knowledge, interpersonal, logistical or financial barriers to LDKT in African American potential recipients.

C. Study Design: We will recruit, enroll and then randomly assign participants to one of three study conditions ("arms"). We will follow participants actively for 1 year to assess the effectiveness of interventions to improve live kidney donation and receipt of LDKT among study participants.

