- c) Following the 14-day opt-out period, study staff will contact potential patient participants, who have not opted out, via telephone to confirm eligibility, answer any questions, review the consent form and obtain verbal consent. (If patients contact us prior to that, they are allowed to take part then.) Study staff will administer the baseline questionnaire. Potential patient participants will be asked to also sign and return the written consent form within the week. We will attempt to remind them to return their signed consent form at future contacts.
- d) Random assignment to intervention arms will take place immediately following completion of the baseline questionnaire while patient participants are on the telephone so they can be informed of their upcoming contacts.
- e) Study staff will mail the DVD and booklet to patient participants randomly assigned to Arms 2 and 3, as well as the TALKS Financial Assistance Program pamphlet and forms to Arm 3 only.
- f) Study staff will mail patient participants a thank you note and \$30 check for completing the baseline questionnaire.

Usual Care (Arm 1)

- h) Patient participants assigned to receive Usual Care (Arm 1) will receive their care at DKPTP as they usually would.

TALK Social Worker Intervention (Arms 2 and 3 only) and Financial Intervention (Arm3 only)

- i) Patient participants randomly assigned to Arms 2 and 3 will be asked to review the 20-minute TALK video and booklet related to living kidney donation, as well as attend two meetings with the study Social Worker to talk about LDKT. If the patient participant says they are unable to attend an in-person meeting due to distance, lack of transportation, or their health issues does not allow them to travel, we will offer the Social Worker meeting (SWI) via telephone. This will not be offered to any patient participant unless they mention the barriers noted above. We will offer this prospectively to newly consented patient participants as well as for those who were consented previously and were unable to take part in the SWI meeting due to these same barriers, (recorded in our database), we will contact them via phone to offer this option.

- j) Study staff will schedule patient participants first meeting with the study Social Worker following the baseline questionnaire and contact them a few days prior to remind them of the meeting and to encourage them to review the DVD and booklet.

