3.1 Primary and Secondary Outcomes

1. Live kidney donor activation (primary): per the protocol, “defined as the composite rate of live kidney donor inquiries on behalf of patient participants, completed live kidney donor transplant evaluations, and live kidney donor transplants in each arm, ascertained via medical records maintained by the Duke Kidney and Pancreas Transplant Program.”

In other words: For each participant, the total number of donor inquiries, evaluations, and LDKT over a 12-month period will be summed and defined as the live donor activation score. For example, if a participant had 5 inquiries, 2 evaluations, and an LDKT, then this person’s score would be 8.

In sensitivity analyses, we will look at these individually, and the composite at 24 months.

2. Pursuit of LDKT (secondary) (scenario): Assessed by two questions, Q1: “Has a family member or friend told you that they would give you a kidney?” And Q2: “Have you talked with family and/or friends about the possibility of someone giving you a kidney?”. Participants will be categorized into 3 groups: 3=identified a donor (answered “yes” to Q1); 2=talked with family members/friends but did not identify a donor (“no” to Q1 and “yes” to Q2); 1=did not talk to family members/friends (“no” to Q1 and Q2). Note that once a person has reached a level, he cannot regress to a previous level, e.g., if at level 2 at randomization, the person cannot be at level 1 at month 4.

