4.2.2 Dichotomous Formulation of Scenario

We will also dichotomize the scenario into maximum activation (talked with family/friends and identified a donor) vs less activation (talked with family/friends but did not identify a donor, or did not talk to family/friends). We will use a similar GEE (binomial outcome) to determine if the probability of having maximum activation over time is different between arms.

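### The scenario GEE tests differences in change with a free baseline mean in each arm, which is valid but usually less precise than a common-baseline or baseline-adjusted comparison of the same data

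*SAP*

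**What the plan says.** SAP 3.1 scores pursuit of LDKT (scenario) from 1 to 3 and states that "once a person has reached a level, he cannot regress to a previous level". SAP 4.2.1 sets the model: "We will model scenario as a continuous variable and use longitudinal GEEs (normal outcome) with an unstructured correlation matrix". The mean has an intercept, two arm terms (β1, β2), two visit terms (β3, β4) and four arm-by-visit terms (β5 to β8). The cell-mean table in that section has β0, β0 + β1 and β0 + β2 in its baseline row, so each arm has a free baseline mean. There is no baseline covariate.

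The stated order of inference is: "We will assess the changes in scenario within each arm, and then determine if there is a difference across arms at 12 months". The arm comparison is read from β7 and β8; for β7, a non-zero value means that "the change from baseline in Arm 2 is significantly different than the change from baseline in Arm 1". SAP 4.2.2 carries a similar GEE over to a dichotomised level.

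Three other facts matter:
- The protocol (Study Phase 2, Study population) plans "100 per each study arm".
- The protocol (Patient Participants, Screening, Recruitment, and Random Assignment, item d) states: "Random assignment to intervention arms will take place immediately following completion of the baseline questionnaire".
- SAP 4.2.3 records that every participant had baseline data.

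The SAP does adjust for a baseline score (blACT) in the Poisson/ZIP section for the primary outcome, but it marks that section as no longer the main approach. Nothing comparable is planned for scenario.

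**The concern.** The baseline level is measured before allocation, so any difference between arms at baseline is chance. Giving each arm its own baseline mean and subtracting it removes that chance difference in full, one unit for one unit. That is the right amount only if participants who start one level higher also finish, on average, one level higher.

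The scale makes this unlikely. A participant at level 3 cannot move, one at level 2 can rise by one, and one at level 1 can rise by two. If those at level 1 move on average at least as far as those at level 2, and anyone moves at all, the slope of 12-month level on baseline level is below 1. Full subtraction then over-corrects and adds noise.

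What is at stake is the precision of one model for the named secondary outcome, with a planned 100 participants per arm. It is not the validity of that model.

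**Working it through.** **Inputs.** From the documents: 100 per arm, visits at baseline, 4 and 12 months, a 1–3 scale without regression, randomisation after baseline, and complete baseline data. Not in the documents: the SDs, the baseline to 12-month correlation ρ, movement rates, effect size, alpha and power for scenario. These are assumed below. There is no sponsor figure to reproduce.

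**Step 1: what β7 estimates.** With complete data, β7 from the saturated model equals the raw difference in mean change; in simulation the two agreed to about 3 × 10⁻¹⁴. The unstructured correlation therefore recovers nothing from baseline. Because the true baseline means are equal, the expected value of β7 is also the difference in 12-month means, so a baseline-adjusted model targets the same quantity.

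**Step 2: variances.** Let s0 and s12 be the SDs at baseline and 12 months, with n per arm.
- Change contrast: (2/n)(s0² + s12² − 2ρ·s0·s12)
- Linear baseline-adjusted contrast: (2/n)·s12²(1 − ρ²)
- Difference: (2/n)(s0 − ρ·s12)², which is never negative and is zero only when the slope ρ·s12/s0 equals 1.

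With s0 = s12 the ratio of adjusted to change variance is (1 + ρ)/2, so the loss is (1 − ρ)/2. The last column takes an effect that has 80% power under the change contrast (two-sided 0.05, assumed).

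| ρ | Variance lost | SE of change contrast larger by | Power after adjustment |
|---|---|---|---|
| 0 | 50% | 41% | 98% |
| 0.2 | 40% | 29% | 95% |
| 0.5 | 25% | 15% | 90% |
| 0.6 | 20% | 12% | 88% |
| 0.8 | 10% | 5% | 84% |
| 0.9 | 5% | 3% | 82% |

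**Step 3: a worked case on the real scale (assumed rates).** Baseline levels 1/2/3 are 30%, 40% and 30%. By 12 months, 40% of level 1 reach level 2, 10% of level 1 reach level 3, and 20% of level 2 reach level 3.
- Baseline: mean 2.00, variance 0.60.
- 12 months: 15%, 44% and 41% at levels 1, 2 and 3; mean 2.26; variance 5.60 − 2.26² = 0.4924.
- Covariance: 4.94 − 2.00 × 2.26 = 0.42. Slope 0.42/0.60 = 0.70; ρ = 0.77.
- Change variance: 0.60 + 0.4924 − 0.84 = 0.2524.
- Adjusted variance: 0.4924 − 0.42²/0.60 = 0.1984.
- Loss: 1 − 0.1984/0.2524 = 21%.

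**Step 4: how far this moves.** Exact enumeration of 9,280 assumed baseline and movement patterns on this scale gave a median ρ of 0.69 and a median loss of 23% (5th to 95th percentile 3% to 50%). Of these settings, 42% fell below a 20% loss and 15% above 40%. These shares describe the assumed grid and are not probabilities.

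**Step 5: fitted models.** In 300 simulated trials of 3 × 100 in a middle case, the empirical SD was 0.0850 for the SAP contrast and 0.0743 for the common-baseline GEE. The variance reduction is 1 − (0.0743/0.0850)² = 24%. For an assumed true difference of 0.20 levels:
- SAP contrast: Φ(0.20/0.0850 − 1.96) = Φ(0.39) = 65%
- Common baseline: Φ(0.20/0.0743 − 1.96) = Φ(0.73) = 77%

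A second set of 400 null trials, in another middle case, gave SDs of 0.0788 (SAP), 0.0672 (common baseline, 27% less variance) and 0.0656 (baseline covariate, 31% less). Null rejection rates were 4.8%, 4.5% and 3.8%, so the gain is not bought with type I error.

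**Step 6: missing visits.** With 20% missing completely at random at each follow-up visit, the simulated ratios of common-baseline to SAP variance were 0.68, 0.77 and 0.85 at ρ = 0.3, 0.5 and 0.7. With complete data they were 0.66, 0.73 and 0.86.

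**The case against.** The strongest defence is that the model fits the stated aim. SAP 1.1.1 asks about scenario movement, and 4.2.1 wants changes within each arm before the arms are compared; a saturated model gives both. This stands as a reason for the layout but not for the free baseline means. A common-baseline model still yields a change for each arm, and its arm contrast has the same target.

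Second, this is one of several analyses of scenario. SAP 4.2 adds cross-sectional tests, 4.2.2 a dichotomised GEE, and 4.2.3 three models of steps forward. That stands: the loss concerns this model, not every look at the secondary outcome.

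Third, the size is not in the documents. That also stands. A reader might infer a firm loss of a fifth to two fifths. With equal variances that needs ρ between 0.2 and 0.6, and the no-regression rule tends to push ρ higher, where the loss is smaller.

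Fourth, the SAP was written with some outcomes known: 4.1.2.4 refers to only four LDKT events, and 4.1.1 to omission from the final manuscript. Replacing the model could look post hoc. This does not defend the contrast, but it governs how the change is made and labelled.

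**Conclusion.** The point holds as one of efficiency. The tested contrast is valid but usually less precise than an alternative that needs no new data. The variance loss is (1 − ρ)/2 under equal variances. With ρ unstated, that is roughly 5% to 50%, and about a quarter in a middle case (power about 65% to about 77% for an assumed 0.20-level difference). These figures rest on assumed baseline distributions and movement rates, 100 per arm and two-sided 0.05.

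A reader might infer more than the documents support:
- That baseline is wasted. It is in the model and is subtracted; it is used inefficiently.
- That the comparison is biased or its type I error inflated. Randomisation follows the baseline questionnaire, so it is neither.
- That the ceiling at level 3 is cured by adjustment. It is not; adjustment only stops the over-correction.
- That the main result is affected. The primary analysis is the time-to-first-event analysis of SAP 4.1.2, which does not use this model.

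The change is worth making, but the trial's conclusions do not depend on it for validity.

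**What to change.** In SAP 4.2.1, do one of the following and name it as the analysis:
- Drop the Arm2 and Arm3 main effects so that all arms share one baseline mean, and keep the four arm-by-visit terms. β7 and β8 then become baseline-adjusted 12-month differences.
- Model the 4- and 12-month levels only, with baseline level as a covariate.

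Keep the present change contrast as a sensitivity analysis and report it alongside. If scenario results have already been seen, label the adjusted model as added later.

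In SAP 4.2.2 use only the common-baseline constraint. The two options are not interchangeable there. Under the no-regression rule a participant at level 3 at baseline stays there, so a baseline-maximum indicator predicts the outcome perfectly and the model separates. In one simulated 3 × 100 trial its coefficient was about 27 with a standard error of about 15,800. Entering level as a linear term avoids separation but makes the arm odds ratio conditional rather than marginal. No precision gain has been computed for 4.2.2.

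The cost is a wording change, two terms removed and one extra reported line. No new data are needed, since every participant has a baseline value.

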4.2.2 Dichotomous Formulation of Scenario

We will also dichotomize the scenario into maximum activation (talked with family/friends and identified a donor) vs less activation (talked with family/friends but did not identify a donor, or did not talk to family/friends). We will use a similar GEE (binomial outcome) to determine if the probability of having maximum activation over time is different between arms.

4.2.3 Number of Steps Forward

The number of steps the participant moved forward at each follow-up visit will also be modeled with a GEE. Of interest is the number of steps moved from baseline to month 4, and from month 4 to month 12. All participants had baseline data. If participant was missing a M4 or M12 value, then 0 steps taken was imputed as the most conservative estimate. If participant was missing a value due to receipt of transplant, then the person was dropped from the analyses at the time of transplant reporting and thereafter.

Participants are not able to go back in scenario, thus if M4 scenario is less than baseline, or if M12 scenario is less than M4 (or baseline) then 0 steps will be imputed.

We will also fit a linear model looking at the total number of steps across the whole study, and a logistic regression model looking at any steps forward across the whole study as an outcome.

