1.2 Study Hypotheses

1.2.1 Primary Hypothesis

Those in the two intervention groups will have higher levels of activation and scenario movement compared to those in usual care.

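### Zero-step imputation is called conservative, but it does not bound the between-arm difference, and no sensitivity analysis is stated for the steps models

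*SAP*

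**What the plan says.** SAP 4.2.3 counts the scenario levels each participant moves forward from baseline to month 4 and from month 4 to month 12. It plans a GEE for steps at each visit, a linear model for total steps and a "logistic regression model looking at any steps forward across the whole study as an outcome".

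Its missing-data rule is: "If participant was missing a M4 or M12 value, then 0 steps taken was imputed as the most conservative estimate". Values missing because of a transplant are treated differently: those participants leave the analysis from that point. The section also records that "All participants had baseline data".

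SAP 1.2.1 gives the hypothesis these models serve: the two intervention groups "will have higher levels of activation and scenario movement compared to those in usual care".

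SAP 3.1 defines three levels and states that "once a person has reached a level, he cannot regress to a previous level". Its one mention of sensitivity analyses concerns the primary activation outcome. For scenario, sections 4.2 to 4.2.2 also plan crosstabs by arm at each time point and GEEs on the level itself and on a dichotomised version. None of these states a zero imputation, and none is presented as a check on it. The SAP cites an appendix that is not among the supplied documents.

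**The concern.** Whether an imputation is conservative has to be judged on the quantity being tested, which here is intervention minus usual care. Lowering both arms by unknown amounts can move their difference either way. A reader told that the estimate is conservative would take a positive steps result as a lower bound on the true effect, which the rule does not guarantee.

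Equal response cannot be presumed. All arms receive the same 4- and 12-month telephone questionnaires with the same $30 payment (Protocol, Patient Participants, Assessments). Only Arms 2 and 3 also have social worker sessions, each followed by a $50 check. That contact could raise response in those arms, or its burden could lower it.

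A separate, smaller point is that the steps models state no adjustment for baseline level, although a participant who starts at level 3 can only score 0.

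**Working it through.** The plan gives no step rate, dropout rate or power for this outcome, so there is no stated figure to reproduce.

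**Inputs.** The planned 100 per arm comes from the Protocol (Study population). Everything else is assumed: the true any-step rate p, the share m missing month 12, the any-step rate q among the missing, the share f of the missing who also miss month 4, and the share h = 0.5 of movers who had moved by month 4. U is usual care and I an intervention arm.

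**Formula.** Apparent any-step rate under the zero rule = p − mq + mq(1 − f)h. If all the missing miss both visits (f = 1), the error in the apparent difference is

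(apparent I − apparent U) − (pI − pU) = mU·qU − mI·qI.

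A positive value favours the intervention.

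**No true effect** (p = 30% in both arms; pooled two-proportion z-test, two-sided 5%, exact binomial enumeration):

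| Missing, U v I | q, U / I | Apparent rates at f = 1 | Rejection at f = 0 / 0.5 / 1 |
|---|---|---|---|
| 25% v 10% | 30 / 30% | 22.5 v 27.0% | 6.4 / 8.3 / 11.3% |
| 25% v 10% | 15 / 15% | 26.25 v 28.5% | 5.4 / 5.8 / 6.4% |
| 25% v 10% | 0 / 0% | 30 v 30% | 5.1% throughout |
| 20% v 10% | 30 / 30% | 24 v 27% | 5.6 / 6.4 / 7.7% |
| 20% v 15% | 30 / 30% | 24 v 25.5% | 5.1 / 5.3 / 5.6% |
| 20% v 20% | 30 / 30% | 24 v 24% | 5.0% (f = 1) |
| 20% v 20% | 40 / 20% | 22 v 26% | 10.1% (f = 1) |
| 20% v 20% | 50 / 10% | 20 v 28% | 26.2% (f = 1) |

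First row at f = 1: 0.30 − 0.25 × 0.30 = 0.225 and 0.30 − 0.10 × 0.30 = 0.270.

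**Break-even.** With f = 1 the rule does not overstate the difference only if qI/qU ≥ mU/mI. That ratio is 0.25/0.10 = 2.5 in the first case and 0.20/0.15 = 1.33 at 20% v 15%.

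**A true effect, both directions.**
- True rates 40% v 50%, missingness unrelated to movement, f = 1. With 20% missing in each arm the gap shrinks to 0.50 × 0.8 − 0.40 × 0.8 = 8 points, which is conservative. With 20% v 10% missing it grows to 0.50 × 0.9 − 0.40 × 0.8 = 13 points.
- True rates 30% v 50%, with 10% v 25% missing and unrelated to movement. The 20-point gap shrinks to 15.3, 12.9 or 10.5 points (f = 0, 0.5, 1), with power 61.5%, 48.6% or 35.9%. Observed cases (90 v 75 participants) give 75.1%.

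**Total steps.** With no effect, mean 0.5 in both arms (probabilities 0.6/0.3/0.1 for 0/1/2 steps) and 30% v 10% missing both visits at random, the spurious difference is 0.5 × (0.30 − 0.10) = 0.10 steps. A simulated t-test rejects 20.3% of the time, against 4.9% for observed cases.

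**Baseline level.** Assume 0/1/2 steps with probability 0.5/0.3/0.2 from level 1, 0/1 with 0.65/0.35 from level 2, and 0 from level 3. The means are 0.70, 0.35 and 0, and the variances 0.61, 0.2275 and 0. The proportional reduction in the variance of the arm effect is between-level variance over total variance:
- Mix 20/60/20% (levels 1/2/3): 0.0490 / (0.0490 + 0.2585) = 15.9%.
- Mix 30/30/40%: 0.0845 / (0.0845 + 0.2513) = 25.2%.

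**The case against.** *The wording may describe only the imputed value.* Read that way, zero is indeed the lowest step count. But the count is imputed to feed a comparison of arms, and the section does not limit the word to the individual value.

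*Observed-case analysis can be worse than the zero rule.* This is true under the same assumptions. With equal 20% missing and non-responders moving at 50% v 10%, responders move at (0.30 − 0.20 × 0.50)/0.80 = 25% and (0.30 − 0.20 × 0.10)/0.80 = 35%. That is a false gap of 10 points against 8, with rejection 28.5% against 26.2%. At 40% v 20% it is 10.8% against 10.1%. With 25% v 10% missing it is 7.7% against 5.4–6.4% if non-responders move at 15%, and 14.7% against 5.1% if they never move; in these last two the error runs against the intervention. This stands as a reason to keep the zero rule and not to rely on observed cases. It does not make the zero rule conservative.

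*The problem is hypothetical and may be small.* This also stands. Every input but the arm size is assumed, mild imbalance leaves the test near nominal, the 50% v 10% case is extreme, and if non-responders truly did not move, zero is correct. Transplant-related missingness also falls outside the rule.

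*Other analyses cover it.* With a plan to "use longitudinal GEEs (normal outcome) with an unstructured correlation matrix", section 4.2.1 estimates an arm difference in change from baseline to 12 months, close to the total-steps contrast. That and the crosstabs are useful partial cross-checks. They state no missing-data rule, and neither varies the assumption about non-responders.

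*Baseline adjustment is unrelated.* It is a separate matter of precision, not a correction of bias.

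**Conclusion.** The concern holds. The rule does not have the property the SAP claims for the between-arm comparison, and the supplied text states no sensitivity analysis for the steps models. That rests on the identity in the working and needs no assumed rate.

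The size does rest on assumptions. At 25% v 10% missing and no true effect, false-positive rates run from nominal to about 11%. Equal missingness with non-responders who move differently by arm can push them higher, and loss concentrated in the intervention arm can cost substantial power. The documents cannot show which case applies, so this does not establish that the trial's steps result is biased.

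The consequence is limited to one formulation of the secondary outcome. The baseline-level point is worth roughly 16–25% lower variance of the arm effect on total steps, if 20–40% of participants start at level 3 and the assumed step probabilities apply.

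**What to change.** - Delete the claim that zero is the most conservative estimate. Keep the zero rule as planned.
- Add two analyses labelled as sensitivity analyses for the steps models: (1) observed cases or multiple imputation; (2) a tipping-point analysis that varies non-responders' movement separately by arm and reports where the conclusion changes. The second directly tests the claim being deleted.
- Report missing month-4 and month-12 values by arm alongside the planned CONSORT diagram.
- Add baseline scenario level as a covariate in the steps models. Level 3 predicts zero perfectly in the any-step logistic model, and in any log-link GEE, so fit these among participants at level 1 or 2 at baseline (a subset defined before randomization) or use a penalised likelihood.

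The cost is one phrase and modest programming. No new data are needed, since baseline level is complete. The first sensitivity analysis assumes data missing at random, the tipping-point range has to be chosen, and adjustment makes the odds ratio conditional on baseline level. SAP 4.1.2.4 already refers to 4 LDKT events, so the additions should be dated and the unadjusted zero-rule result still reported.

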4.1.2 Primary Approach: Time to First Event Survival Analyses

Note that this section is the PRIMARY approach in the manuscript.

4.1.2.1 12-month composite activation

Outcome: We will use survival analysis techniques to model time to first activation event (inquiry, evaluation, or LDKT) in the presence of two competing risks: deceased donor transplant (DDKT) and death.

Censoring: Participants will be censored if they did not have an activation event during the observation period. Participants with no event before withdrawing from the study will be censored at their withdrawal date; all others with no event will be administratively censored at 12 months after randomization.

Standard survival methods do not work in the presence of competing risks because the assumption that censoring is independent is violated.

Independent censoring means that individuals who are censored have similar risk of the event of interest as those still in the study, but this is not the case for competing risk – if a person dies, that person no longer is at risk of having a donor inquiry or transplant, for example. Standard survival analyses will often overestimate the probability of the event of interest.

The competing risk framework can also be used in our case with nonfatal, semi-competing risks, if interest lies in which event type occurred first. We will use this logic for the analyses of our outcome.

We will use the cumulative incidence function (CIF) to estimate incidence of

occurrence of an activation event in the presence of competing risks. We will also fit subdistribution and cause-specific Cox proportional hazard models. Let $k = 3$ be the number of competing risks: activation event, DDKT, and death. The CIF for the k th event is defined as $\text{CIF}_k(t) = P(T \leq t, K = k)$, the probability of experiencing the k th event before time t and before the occurrence of one of the other events. This will be plotted both overall and by arm.

We will then investigate the subdistribution hazard function, defined as

$$\lambda_k(t) = \lim_{\Delta t \rightarrow 0} \frac{P(t < T \leq t + \Delta t, K = k | T > t \cup (T < t \cap K \neq k))}{\Delta t}$$

This is the “instantaneous *risk of failure* from the k th event in subjects who have not yet experienced an event of type k .” This risk set include those who are event free and *those who have experienced a competing event*.

In contrast, the cause-specific hazard functions for each event is defined as

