$$\lambda_k(t) = \lim_{\Delta t \rightarrow 0} \frac{P(t \leq T < t + \Delta t, K = k | T \geq t)}{\Delta t}$$

This is the instantaneous *rate of event k* at time t , in subjects *who have experienced none of the events* (of any type) before time t .

Both subdistribution and cause-specific hazard models will be fit, having the form

$$\lambda_k(t) = \log\{\lambda_{k0}(t)\} + \beta_1(\text{arm2}) + \beta_2(\text{arm3}).$$

Here, $\lambda_{k0}(t)$ denotes the hazard function for participants in arm 1, and “arm2” and “arm3” are indicator variables. Interest lies in β_1 and β_2 , the increased hazard of each event being in the intervention arms compared to the control arm.

4.1.2.2 12-month donor inquiry alone

A similar survival approach described above will be used to model time to first inquiry (ignoring evaluations and LDKTs) in the presence of the competing risks DDKT and death.

4.1.2.3 12-month donor evaluation alone

A similar survival approach described above will be used to model time to first evaluation (ignoring inquiries and LDKTs) in the presence of the competing risks DDKT and death.

4.1.2.4 12-month LDKT

Though it is likely not possible or even meaningful with only 4 events, a similar survival approach will be used to model time to LDKT (ignoring inquiries and evaluations) in the presence of the competing risks DDKT and death.

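### The steps-forward analysis drops participants whose value is missing because of any transplant, without separating live donor transplants, which the trial counts as success, from deceased donor transplants

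*SAP*

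**What the plan says.** The scenario outcome (SAP 3.1, item 2) has three levels, and the top one is defined as follows: "Participants will be categorized into 3 groups: 3=identified a donor". A participant reaches it by answering yes to the question "Has a family member or friend told you that they would give you a kidney". The SAP adds that "once a person has reached a level, he cannot regress to a previous level".

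SAP 4.2.3 models the number of levels gained between visits and has two rules for missing data:

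- **Ordinary missing visit:** "If participant was missing a M4 or M12 value, then 0 steps taken was imputed as the most conservative estimate".
- **Missing because of a transplant:** a participant "missing a value due to receipt of transplant, then the person was dropped from the analyses at the time of transplant reporting", and stays out thereafter.

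The second rule does not mention donor type, and no other section makes an exception for LDKT in the scenario analyses. SAP 4.2.1 and 4.2.2, the continuous and dichotomous formulations, state no rule for missing visits. In SAP 4.1.2 the two transplant types are treated differently: LDKT is one of the three activation events, while DDKT and death are the competing risks.

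**The concern.** For a DDKT, dropping the participant is defensible, because looking for a live donor has become moot. For an LDKT the same rule discards a value that can usually be inferred. If the donor was a family member or friend, the participant has reached level 3 whether or not the questionnaire was completed.

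The two rules are also uneven. A participant who simply misses the visit stays in with 0 steps. A participant at level 1 who receives an LDKT before month 4, and misses the later questionnaires for that reason, contributes no steps and leaves the denominator.

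Removal thus depends on an event after randomisation that the interventions are designed to make more frequent. Scenario movement is a secondary outcome, but SAP 1.2.1 names it alongside activation in the hypothesis that the intervention arms will do better than usual care. The randomised comparison should not lose people because they succeeded.

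**Working it through.** The plan gives no figure tied to this rule, so there is nothing to reproduce. The possible effect can be bounded.

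**Inputs from the documents**

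- LDKTs within 12 months: 4. SAP 4.1.2.4 says of modelling them: "Though it is likely not possible or even meaningful with only 4 events".
- Planned size: 300 participants, 100 per arm (Protocol, Study population).
- Steps to level 3: 2 from baseline level 1, 1 from level 2, 0 from level 3 (SAP 3.1).

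**Assumptions, because the documents do not give these values**

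- All k = 4 recipients are in one arm of n = 100, and all have the value missing because of the transplant.
- The other 96 in that arm have mean steps m between 0.1 and 0.5, or a proportion p between 0.1 and 0.5 with any step forward.

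**Share affected.** 4/300 = 1.3% of the planned sample, or 4/100 = 4% of one arm.

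**Mean steps.** With the recipients dropped, the arm mean is m. With each counted at s steps, it is ((n − k)m + ks)/n. The shift is k(s − m)/n.

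| Baseline level | s | m = 0.1 | m = 0.5 |
|---|---|---|---|
| 1 | 2 | 4 × 1.9/100 = +0.076 | 4 × 1.5/100 = +0.060 |
| 2 | 1 | 4 × 0.9/100 = +0.036 | 4 × 0.5/100 = +0.020 |
| 3 | 0 | 4 × (−0.1)/100 = −0.004 | 4 × (−0.5)/100 = −0.020 |

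**Any step forward.** If all 4 had a step left to make, the proportion rises by k(1 − p)/n. That is 4 × 0.9/100 = 3.6 percentage points at p = 0.1 and 4 × 0.5/100 = 2.0 points at p = 0.5.

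**One LDKT in the arm instead of four.** The mean shifts by at most 1 × 1.9/100 = 0.019 steps, and the any-step proportion by at most 1 × 0.9/100 = 0.9 points.

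The mean-steps formula applies to a single interval in the GEE. It applies to the whole-study total only if that model drops the same people, which the SAP does not say.

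**The case against.** The strongest reply is that the scenario is a self-reported questionnaire outcome, at most 4 people are involved, and LDKT success is already captured by the primary composite and by its own analysis in SAP 4.1.2.4. All of this is true, and it limits the point to one formulation of a secondary outcome. It does not explain why two transplant types that the SAP separates elsewhere are merged here.

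A reader might also infer more than the documents support:

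- **That the missing value is always known.** Level 3 rests on an offer from a family member or friend. An LDKT from any other donor does not by itself satisfy the question.
- **That the rule must bias toward no effect.** It does so only if LDKTs are more frequent in the intervention arms among people with steps left to make. A recipient already at level 3 adds 0 steps, so dropping that person slightly raises the arm mean. Offers before randomisation are plausible, since SAP 4.1.1.1 defines a baseline activation score from earlier inquiries and evaluations.
- **That the arm mean loses 0.04 to 0.08 steps** (4 × 1/100 to 4 × 2/100). This treats dropped people as if they stayed in with 0 steps. They leave the denominator too, so the shift is smaller.
- **That every LDKT recipient's movement is lost.** The drop applies only where the value is missing because of the transplant, and only from transplant reporting onward. A step recorded at month 4 before a later transplant stays in the GEE.
- **That the whole-study models and SAP 4.2.1 and 4.2.2 share the loss.** This is a natural reading of the former and a likely result of fitting a GEE to available visits in the latter, but neither is stated.

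**Conclusion.** The point holds as an internal inconsistency. SAP 4.2.3 excludes participants for a reason tied to success, treats LDKT and DDKT alike where the primary analysis does not, and discards values that the no-regression rule usually allows to be filled in.

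The practical effect is small: within 12 months at most 4 participants, a mean shift below 0.08 steps, and an any-step shift below 4 percentage points, even with all 4 in one arm. The direction cannot be settled from the documents, because the split by arm, the baseline levels and the number with values missing because of the transplant are not given. The bounds rest on the planned 100 per arm and on the assumed ranges for m and p. The primary time-to-first-event analysis is not affected. The change is worth making because it costs little and removes an outcome-dependent exclusion, not because the result is likely to turn on it.

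**What to change.** In SAP 4.2.3, split the transplant rule by type:

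- **LDKT in the program records:** set the scenario to 3 at visits missing after the transplant and count the resulting steps (0 if already at level 3). State an exception for donors who are not family or friends.
- **DDKT:** keep the present drop.

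State that the whole-study total-steps and any-step models follow the same rule. Use the same value in SAP 4.2.1 and 4.2.2, so that the formulations agree. Report the number dropped by arm and transplant type, which will show the actual impact.

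The cost is a few sentences in the SAP and a merge of LDKT dates that SAP 4.1.2.4 already needs. The SAP does not say whether the data pull records the donor's relationship to the recipient, but with 4 recipients this is a short check. The downside is that a few questionnaire values are filled from medical records. The result under the present rule can be kept as a sensitivity analysis.
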